- After the visit, each patient will complete a post-visit survey assessing their demographics, their contraceptive methods choice and their opinion of the counseling they received. If the patient must leave the clinic without completing her post-visit survey due to time constraints (and not because she wishes to withdraw from the study), study personnel will attempt to contact the patient using the contact information given at the time of the visit and have them complete the post-visit survey by phone or email. If the patient does not complete the post-visit survey within 48 hours of their initial visit, study personnel will continue to attempt to have them complete the post 48-hours version of the post-survey (in which the time-sensitive questions have been omitted) up to one month after the initial visit.
- Study staff will provide each patient with a flyer summarizing the timing of follow-up and with contact information for study staff in case participant changes her contact information or wishes to dis-enroll.

1. Patient Follow-Up Survey

Each patient will be contacted by whatever method they prefer (phone, mail, SMS, email) at four and seven months after the visit to complete a follow-up survey to assess whether they have continued their contraceptive method. The survey can be completed either over the phone with an RA or on the patient's own time online using REDCap.

- Patient contact information and enrollment dates will be entered into REDCap, where follow-up contact due dates will be calculated. RAs and volunteers will conduct follow-up attempts via the patient's preferred method, logging each attempt and its outcome in REDCap.
- In order to accurately assess whether Depo users got their next shot on time, 4 month follow up calls will begin at 112 days (16 weeks) and 7 month follow up calls will begin at 217 days (31 weeks).
- The secure UCSF email address [contact] has been created and added to each RA's email account to facilitate participant follow-up by multiple people.

Study Protocol

Patient Centered Support for Contraceptive Decision-Making: A Cluster Randomized Controlled Trial of a Contraceptive Decision-Support Tool

November 22, 2016

- Google Voice will be used for text and phone follow-up contact attempts. Contact information will be deleted from the program monthly.

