	Pre-intervention	Post-intervention	Follow-up interview/recording (intervention arm only)
Demographics	X		
Provider burnout	X	X	
Provider/patient engagement in shared decision-making, measured qualitatively	X		X

B. Sample Size:

Specific Aim 1: We based our sample size calculation on our primary outcome, contraceptive continuation. Based on our previous studies in this population, we estimate that 50% of women in our control group will continue with their contraceptive method at seven months. Using this same data, we have calculated the intra-cluster correlation (ICC) of this response by provider and by clinic at ~0 and 0.021 respectively. Accounting for clustering and 20% loss to follow-up, as well as a inflation factor to account for differences in contraceptive initiation among those in clinics with IUDs and implants on-site as compared to those without these methods on site, a sample of 758 patients (approximately 32 patients for each of 24 providers) would provide 80% power in 2-sided tests with a type-I error rate of 5% to detect a 12 percentage point increase in continuation, to 62%. This difference in contraceptive continuation would be clinically meaningful and is consistent with effects reported in the contraceptive literature. Again using data from our previous study to estimate ICCs and baseline parameters, the sample will also provide 80% power to detect small-to-moderate but clinically significant differences in secondary outcomes as shown below.

Study Protocol

Patient Centered Support for Contraceptive Decision-Making: A Cluster Randomized Controlled Trial of a Contraceptive Decision-Support Tool

November 22, 2016

Outcome	ICC		Design effect	Baseline SD/%	SES/ MDD
	Clinic	Provider			
Continuous measures					
Decision conflict scale	0.000	0.027	1.3	1.9	0.25
Satisfaction score	0.152	0.075	1.7	6.5	0.31
Dichotomous measures					
Choice of highly effective method	0.096	0.000	0.9	23%	10.9%
Shared decision making	0.006	0.024	1.3	46%	14.3%
Unintended pregnancy	0.005	0.001	1.0	5%	-4.5%
For continuous outcomes, the standard deviation (SD) and standardized effect size (SES) are reported; for binary outcomes, the baseline prevalence and absolute effect, both in percent.					

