Analysis Plan: Patient Centered Support for Contraceptive Decision-Making: A Cluster Randomized Controlled Trial of a Contraceptive Decision-Support Tool

Principal Investigator: [name] MAS

Intention-to-treat analysis

Participants who “cross over” from their assigned study arm (as determined by the provider they are likely to see) will be included in the final analyses in the arm in which they were initially assigned.

Modified intention-to-treat analysis: Post-randomization exclusion

Some participants may be excluded from analysis after being randomized:

- Participants who find out they are pregnant during their enrollment visit (and thus would have been ineligible had this been known prior to enrollment).
- Participants who enrolled in the study more than once (their second enrollment will be excluded).

Data Collection and Analysis

The outcomes of interest for this study have been divided into three specific aims, which dictate what type of data is collected and how it is analyzed.

Outcomes of Interest

Specific Aim 1: The primary outcome is a binary indicator of contraceptive continuation at 7 months and a secondary outcome is a binary indicator of contraceptive continuation at 4 months. For ambiguous cases for these outcomes, we used a blinded adjudication process and applied a standardized list of rules and assigned outcomes throughout the process of data collection. Potential outcomes for individuals are as follows: continuous users of chosen method, non-continuous users of chosen method, and missing but included and imputed.

For all variables, the analysis will use multiple imputation to deal validly with the missing values. Of note, specific variables were not collected from participants we collected data from more than 48 hours after their visit. Those variables will be analyzed in the same way as other missing outcomes.

- **Primary outcome:**

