 - Did not have a gap of 4+ weeks during which they were sexually active and did not use a Tier 1 or Tier 2 method at any point since enrollment for four weeks or more OR
 - Report that they discontinued the method at the time of their survey BUT are not using anything else, have not had sex since discontinuation and say they would use this method if they were to have sex (note: no participants met this criteria) OR
 - Never started the method but haven't had sex since enrollment and would use the method if they started having sex (note: no participants met this criteria)
- **Secondary outcomes:**
 - Patient Contraceptive Counseling Satisfaction at post-visit survey
 - Factor analysis-validated survey created by the PI to assess patients' satisfaction with the contraceptive counseling experience.

- In primary analysis, we will do top-scoring of the IQFP total score, i.e. a score of 55 versus all other scores
- Patient Chosen Contraceptive Method Satisfaction at the post-visit survey, and 4 and 7 months
 - 5-point Likert scale question regarding patient satisfaction with contraceptive method chosen.
 - In primary analysis, we will do top-scoring for this questions
 - **Note:** Slightly different questions at baseline and follow-up:
 - 1) Baseline: How satisfied are you with your choice of birth control today?
 - 2) 4mo and 7mo: how much you agree with statement “I chose the best method for me at the time”
- Experience with Shared Decision-Making (measured at post-visit survey)
 - Patient report of having engaged in shared decision making with their provider and their experience with the decision making process, as well as qualitative coding of contraceptive counseling visits. The qualitative coding will focus on the presence or absence of shared patient-provider decision making and patient engagement in the decision making process, drawing on concepts from observational measures of shared decision making, as well as insights into the counseling process gained through our previous observational study.
 - For the question regarding who made decision, we will collapse the responses into 3 categories
 - 1) Health care provider AND mostly health care provider
 - 2) Me and provider equally
 - 3) Mostly me AND me alone
 - For the question regarding whether the provider had a preference:
 - 1) “no preference” vs. other 4 categories

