 - For the 5-point Likert scale question regarding satisfaction with support provided/how the provider helped you to choose, we will do top scoring
 - For the question regarding satisfaction with involvement of provider in the decision making process, we will analyze using the existing three categories (no collapsing)
 - For the question regarding satisfaction with the degree to which provider expressed preference, responses will be collapsed into 3 categories:
 - 1) A lot less strongly AND less strongly
 - 2) Exactly right
 - 3) A little bit more strongly AND a lot more strongly
- Patient Decisional Conflict in Contraceptive Choice at the post-visit survey

- Validated survey to assess patients' decisional conflict in medical decision making.
 - In primary analysis, we analyze this scale as a continuous variable. We will dichotomize if this violates linearity assumptions.
- Patient Current Contraceptive Method Satisfaction at 4 and 7 months
 - 5-point Likert scale question regarding patient satisfaction with the contraceptive method they are currently using.
 - In primary analysis we will do top-scoring, i.e. a score of 5 versus all other scores
- Patient Attitudes and Knowledge of Contraceptive Options and Features (post-visit survey)
 - Patient report of perceived knowledge of their options and questions derived from National Survey of Reproductive Contraceptive Knowledge and previous studies of contraceptive knowledge and attitudes.
 - In primary analysis:
 - Will analyze each of these questions independently. For the questions related to effectiveness and the questions related to knowledge of IUDs, we will also analyze as either answering all questions correctly vs. answering any incorrectly, and also examine the number correct as an ordinal outcome.
 - For all knowledge and attitudes question, unless otherwise specified below, we will analyze answered correctly vs. incorrectly or I don't know
 - Emergency contraceptive knowledge question:
 - 1) Primary analysis: selection of emergency contraception AND copper IUD vs. not selecting both of those
 - 2) Sensitivity analysis: for having copper IUD in their answer vs. not
 - For the "Heard of" question: we are pre-specifying interest in responses regarding IUDs (analyzed together), implant, vasectomy, female sterilization, patch, and ring, with a primary interest in IUDs
 - 1) IUD primary analysis: heard of an IUD (either one) vs. not having heard of it
 - 2) Equivalent analyses for other methods

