We will assess imbalance by treatment assignment using cross-tabulations and comparisons of within group means and medians. Inference for balance on provider covariates will use chi-squared, Fisher's exact, t, and Wilcoxon tests as appropriate, while differences in patient characteristics will be assessed using mixed effects models with fixed effects for clinic and random effects for provider. [IR-3] Primary analyses of treatment effects will be intention-to-treat, according to treatment assignment, and without regard to use of the tool or seeing an intervention provider. Treatment effects will be estimated using mixed effects linear, logistic, proportional odds, and multinomial models, with fixed effects for clinic and random effects for provider.

Missing data. [MD-1] Missing data will have been minimized by active follow-up of participants. [MD-4] Missing data rates for primary and secondary outcomes as well as important covariates will be reported, in combination with summaries of the reasons for missingness, including dropout and pregnancy. [MD-2] All analyses will handle missing data using 20-fold multiple imputation of missing outcomes, based on iterative chained equations. [MD-3] Summary effect estimates, averaged over the 20 imputed datasets, as well as confidence intervals and p-values, will be calculated using standard methods that account for imputation error.

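### The 80% power stated for counselling satisfaction belongs to a continuous score, but the planned main analysis compares the proportion scoring 55

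*SAP*

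**What the plan says.** Protocol section VII.B (Sample Size) states that "the sample will also provide 80% power to detect small-to-moderate but clinically significant differences in secondary outcomes", and a table follows. The satisfaction score is one of two rows under the continuous measures: clinic ICC 0.152, provider ICC 0.075, design effect 1.7, SD 6.5, effect 0.31. The table note reads "For continuous outcomes, the standard deviation (SD) and standardized effect size (SES) are reported"; binary outcomes are given a baseline prevalence and an absolute effect instead. The three binary rows are choice of a highly effective method, shared decision making and unintended pregnancy. None is for top-scored satisfaction.

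The SAP, under Secondary outcomes (Patient Contraceptive Counseling Satisfaction), says: "In primary analysis, we will do top-scoring of the IQFP total score, i.e. a score of 55 versus all other scores". It names no analysis of the full score. The matching entry in protocol section VII.A does not mention top-scoring. Both documents carry the date November 22, 2016.

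The other continuous row, decisional conflict, is planned on the scale on which it was powered: "In primary analysis, we analyze this scale as a continuous variable". That match is conditional, because the SAP's next sentence allows the scale to be dichotomised.

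**The concern.** A power statement holds for one test of one effect. The table's figure is for a difference in means of 0.31 × 6.5 = 2.0 points. The planned analysis compares two proportions, and its power depends on the share of control patients scoring 55 and on how strongly that indicator clusters by provider. The plan gives neither.

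Aim 1 names women's experience of counselling, and this score is one of its direct measures. If the top-score comparison is inconclusive, a reader may set it against 80% power to detect 0.31 SD, which was never worked out for that comparison. Nor can the reader tell what percentage-point difference the trial could detect.

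**Working it through.** **Which score the row describes.** The table says only satisfaction score. A 1-to-5 item cannot have an SD above 2, so an SD of 6.5 rules out the single Likert items. I take the row to be the IQFP total. This is an inference.

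**Inputs.** N = 758, 24 providers, about 32 patients each, two-sided 5% level (Protocol VII.B; the level is stated for the primary outcome and assumed for the table). Arms are 1:1. The design effect of 1.7 is taken as given. The planned sample is described as "Accounting for clustering and 20% loss to follow-up", a loss stated for the seven-month outcome; 758 × 0.8 = 606. Satisfaction comes from the "post-visit survey assessing their demographics, their contraceptive methods choice and their opinion of the counseling they received", so 758 is the upper bound. I keep 606 as a lower bound because "specific variables were not collected from participants we collected data from more than 48 hours after their visit", and the documents do not list those variables.

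**The plan's own figure.** For the continuous score, power = Φ(0.31 × √(N/1.7)/2 − 1.96).
- N = 606: Φ(0.31 × √356.5/2 − 1.96) = 83.3%.
- N = 758: Φ(0.31 × √445.9/2 − 1.96) = 90.5%.
- N = 606 with a t reference on 24 − 2 = 22 df: 79.9%.

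The table's 80% is thus reproduced as a comparison of means.

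**The planned test.** With m = N/(2 × 1.7) effective patients per arm (178.2 or 222.9), power = Φ((p2 − p1)/√[(p1q1 + p2q2)/m] − 1.96), where q = 1 − p. The control share p1 is my assumption. The intervention share p2 depends on what 0.31 SD means for a score with a ceiling:
- Reading A: the score is a normal variable capped at 55, and the observed mean difference is held at 0.31 of the control SD.
- Reading B: 0.31 SD is a shift of the uncapped score, so p2 = Φ(Φ⁻¹(p1) + 0.31).

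Worked case, p1 = 30%, N = 606:
- A: p2 = 0.438, so 0.138/√(0.456/178.2) = 2.73 and power = Φ(0.77) = 78%.
- B: p2 = Φ(−0.524 + 0.31) = 0.415, so 0.115/√(0.453/178.2) = 2.28 and power = Φ(0.32) = 63%.

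| Control share at 55 | p2, A | Power A, N = 606 / 758 | p2, B | Power B, N = 606 / 758 |
|---|---|---|---|---|
| 20% | 31.0% | 67 / 77% | 29.7% | 57 / 67% |
| 30% | 43.8% | 78 / 86% | 41.5% | 63 / 72% |
| 40% | 55.7% | 85 / 92% | 52.3% | 65 / 74% |
| 50% | 66.9% | 91 / 96% | 62.2% | 65 / 74% |
| 70% | 87.0% | 98 / 99% | 79.8% | 57 / 67% |

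Under A, the binary test overtakes the continuous one at a control share of about 37%. That crossover comes from the model: holding the observed effect at 0.31 SD needs an underlying shift of 0.35 SD at a 20% share, 0.44 at 50% and 0.60 at 70%. Under B there is no crossover. B is not a pure cost of dichotomising either, since the ceiling would also shrink the observed mean difference below 0.31 SD.

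**Detectable difference.** Solving the same formula for 80% power over shares of 20-70% gives 12.5-14.7 points (N = 606) or 11.3-13.1 points (N = 758).

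**Sensitivity to the design effect.** With provider ICC 0.075, clinic ICC 0.152 and 606/24 ≈ 25.3 patients per provider, 1 + 24.3 × 0.075 − 0.152 ≈ 2.7. At 2.7 the continuous analysis with N = 606 would have 64% power, and the detectable differences above would be larger. The value of 1.7 fits about 12 patients per provider: 1 + 11 × 0.075 − 0.152 = 1.67. That is a separate question, but it limits how far any of these figures can be relied on.

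**The case against.** The strongest reply is that no harm is shown. The sample size was set on contraceptive continuation, and this is one of about a dozen secondary outcomes. The table labels its row continuous and never claims 80% power for top-scoring. The confidence interval will show the precision achieved. All of that is correct and keeps the point modest. It does not remove the mismatch: the row is offered as the power for this outcome, and the SAP plans no analysis to which it applies.

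A reader might infer that top-scoring leaves the outcome underpowered. The documents do not support that. The two readings above point in different directions at larger shares, and nothing in the plan chooses between them. A reader might also infer that the cut-point was picked after looking at scores. The SAP does record that no participants met certain continuation criteria, so some follow-up data had been reviewed, but that says nothing about satisfaction scores.

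Two further objections stand in part. The row's identity as the IQFP total is inferred: an SD of 6.5 excludes a 5-point item but does not prove that the earlier study used the same 55-point form. And an added full-score analysis enlarges an already long list of secondary results, which is why it should be supportive only.

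**Conclusion.** The mismatch is real and needs no model to see: 80% power is stated for a difference in means, and the main analysis is a difference in proportions. The direction and size of any change in power are unknown. At design effect 1.7, N = 606 and control shares of 20-70%, power runs from about 57-65% (shift of the underlying score) to 67-98% (observed effect held at 0.31 SD), against 80-83% for the continuous analysis by the t and normal calculations. These ranges rest on assumed shares, a normal underlying score, 1:1 arms, and a design effect carried over unchanged from the continuous row. Confidence is high in the mismatch and low in any single power figure. Power for the primary outcome is not affected.

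**What to change.** Do one of two things in Protocol VII.B. Either state that the 80% figure applies only to a continuous analysis of the satisfaction score, or replace the row with the expected share scoring 55, the ICC and design effect of that indicator, and the detectable difference in percentage points. The trial statistician should recompute these. About 11-15 points is illustrative only, for shares of 20-70% with a design effect of 1.7, and would be larger with a higher one. The row should also name the instrument.

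Keep 55 versus all other scores as the main analysis; changing it this late could look data-driven. Add one full-score analysis of the IQFP total, labelled supportive, chosen in advance from the models the SAP already lists under Methods of Analysis, Specific Aim 1: "mixed effects linear, logistic, proportional odds, and multinomial models". Proportional odds is a natural candidate.

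The cost is a sentence or a table row plus one model. The downside is one more secondary result, added late, that depends on its model assumptions (for proportional odds, a common effect across many score levels).

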- 6) A final screen that allows women to print out their method preferences (#2), relevant medical history (#3), questions they wish to ask their health care provider (#5), and the methods that they are most interested in. This print-out is designed to be shared with the medical provider.

B. Study Aims

Our aims are as follows:

Aim 1: To determine the impact of the implementation of a contraceptive decision support tool on women's contraceptive continuation and their experience of receiving contraceptive counseling, including decisional conflict, compared to women receiving usual care.

Aim 2: To qualitatively compare the contraceptive counseling provided to patients who have used the decision support tool prior to their visit and those who have not use the tool.

Aim 3: To assess the experience of providers and health care delivery systems with use of the intervention in the clinical setting.

This study is funded by the Patient-Centered Outcomes Research Institute contract number CE-1304-6874. Study activities will follow [name] Operating Procedures for all procedures not detailed in this study protocol.

Study Protocol

Patient Centered Support for Contraceptive Decision-Making: A Cluster Randomized Controlled Trial of a Contraceptive Decision-Support Tool

November 22, 2016

II. Study Design

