Sensitivity analyses. [MD-5] Because informative missingness would violate the covariate-dependent missing at random (CDMAR) assumption of the standard multiple imputation procedure, we will conduct sensitivity analyses in which we multiply impute missing data under plausible informative missing data mechanisms – in particular, lower contraceptive continuation rates among participants with missing values of this outcome, in one or both arms. [DR-3] In addition, we will conduct sensitivity analyses controlling for any imbalanced pre-randomization characteristics (e.g., age and parity) that predict outcomes, using 5% changes in the coefficient for the intervention as the criterion for covariate inclusion in the adjusted model. To characterize the influence of individual providers, we will estimate best linear unbiased predictions of the provider effects, and also fit models with additional random provider-intervention interactions, to capture heterogeneity in the effects of the intervention. In all analyses, we will transform continuous outcomes as necessary to meet the normality assumption, model departures from linearity in the influence of continuous covariates, check for influential points, and identify potentially important interactions.

Heterogeneity of treatment effects. [HT-1] We will assess modification of the effect of assignment to the intervention by the following 5 pre-specified factors: age, race/ethnicity, language, parental education, and clinic. We will assess evidence for effect modification by adding the effect modifier and its interaction with the treatment assignment indicator to the primary analysis models specified above. To limit inflation of the type-I error rate, we will only estimate within-stratum treatment effects if the interaction is statistically significant at a Bonferroni-corrected $P = 0.01$, and will cautiously interpret findings. These analyses will use multiply imputed data and corresponding inference methods.

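### The dichotomisation fallback for decisional conflict has a trigger that does not fit the model, no cut-point, and no stated order relative to the plan's transformation rule

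*SAP*

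**What the plan says.** The SAP entry for this outcome (Secondary outcomes, Patient Decisional Conflict in Contraceptive Choice) reads: "In primary analysis, we analyze this scale as a continuous variable. We will dichotomize if this violates linearity assumptions". It gives no diagnostic, no threshold and no cut-point.

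The general rule is in the SAP, Methods of Analysis, Specific Aim 1, under Sensitivity analyses: "In all analyses, we will transform continuous outcomes as necessary to meet the normality assumption". The same sentence treats linearity as a separate matter that concerns predictors: "model departures from linearity in the influence of continuous covariates". Protocol VII.C carries the same text. Neither document says which rule governs decisional conflict.

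Treatment effects come from mixed linear, logistic, proportional-odds and multinomial models, with clinic as a fixed effect and provider as a random effect. The SAP's pre-specified covariates, including age, are all categorised.

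Aim 1 in the protocol covers continuation and "their experience of receiving contraceptive counseling, including decisional conflict, compared to women receiving usual care". The table in Protocol VII.B sizes the "Decision conflict scale" as a continuous measure only: provider ICC 0.027, design effect 1.3, SD 1.9, standardised effect 0.25.

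**The concern.** Linearity is a property of the relation between an outcome and a continuous predictor. With a binary arm, clinic indicators and banded covariates there is no such relation to fail, so read literally the trigger cannot be evaluated. What can fail is the distribution of the residuals. If that is what is meant, two instructions cover the same event: transform the scale, or cut it in two. They give different estimands and can give different conclusions.

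The cut is also left open. Elsewhere the SAP fixes its cuts in advance: 55 on the counselling satisfaction total, 5 on current-method satisfaction, below 10 on the unplanned-pregnancy measure. Here it would be chosen once the score distribution is known. At stake are the interpretability of an outcome named in Aim 1 and, if the fallback is used, the power claimed for it.

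**Working it through.** **Inputs.** From Protocol VII.B: 758 patients, design effect (DE) 1.3, standardised effect 0.25, 80% power, two-sided 5% (stated for the primary outcome and assumed for the table), and 20% loss (stated for the 7-month outcome; loss at the post-visit survey is not given). The documents do not give the mean, range, floor rate or skewness of the scale.

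**1. The plan's own figure.** Detectable effect = (1.96 + 0.84) × √(4 × DE / N).
- N = 758: 2.80 × √(5.2/758) = 0.232
- N = 606 (758 × 0.8): 2.80 × √(5.2/606) = 0.260
- N = 655: 2.80 × √(5.2/655) = 0.250

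The printed 0.25 lies between full follow-up and 20% loss, and about 14% loss gives it exactly. It is not shown to be wrong, so I take 80% power at 0.25 SD as stated.

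**2. Loss from a split if scores are near normal.** For a cut at quantile q, the share of information kept is E = φ(z_q)² / [q(1 − q)]. Then power = Φ(2.80√E − 1.96), the detectable effect is 0.25/√E, and the required sample is multiplied by 1/E. The design effect is assumed to be the same for the binary form.

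| Cut | E | Loss | Power at 0.25 SD | Detectable effect | N multiplier |
|---|---|---|---|---|---|
| 50/50 | 0.3989²/0.25 = 0.637 | 36% | Φ(0.275) = 61% | 0.313 SD | 1.57 |
| 20/80 | 0.2800²/0.16 = 0.490 | 51% | Φ(0.00) = 50% | 0.357 SD | 2.04 |
| 10/90 | 0.1755²/0.09 = 0.342 | 66% | Φ(−0.32) = 37% | 0.427 SD | 2.92 |

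A direct two-proportion calculation at 252 per arm (the number that gives 80% at 0.25 SD without clustering) agrees: 61% for the median split, and 53% or 46% for 20/80 depending on which tail is cut.

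**3. Other shapes.** These were simulated at 252 per arm, ignoring clustering. The distributions are assumptions, since the documents give none. The rank test stands in for the proportional-odds model.

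| Shape | t-test | Rank test | Median split | 20/80 split | Cut at floor |
|---|---|---|---|---|---|
| Exponential, effect 0.25 SD | 81% | 69% | 55% | 62% | – |
| Floor spike, 40% vs 52% at the lowest score, several shapes above it | 35–58% | 68–70% | 53–67% | about 22% | about 79% |

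Under plain skew, both splits lose to the t-test and to the rank test. Under a floor spike, a cut at the floor beats both, the median cut does not beat the rank test, and the 20/80 cut does badly. The unspecified cut alone moves power from about 22% to about 79%.

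**4. The two rules side by side.** The outcome-specific sentence has linearity as its trigger and a split as its action. The general sentence has non-normality of the outcome as its trigger and transformation as its action. On a literal reading the first never applies. On the sensible reading both apply at once, and no order is given.

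**The case against.** The strongest reply has four parts.

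First, the two triggers are worded differently, and the outcome-specific sentence can be read as an exception to the general rule or as the step after transformation has failed. That stands: a reader might infer a flat contradiction, but the documents show only an overlap that nobody has resolved.

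Second, the 36% to 51% loss is a normal-theory figure, while the fallback is meant for data that break the model. That stands too. A reader might infer that the plan gives up this share of information outright. It does not: the figure needs near-normal scores and a cut between 50/50 and 20/80, and under a floor effect a well-placed cut gains power. The reply does not rescue the sentence, because the gain depends on a cut that the SAP does not name.

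Third, Protocol III.B.3 keeps staff blinded during quantitative analysis. This prevents a choice driven by the arm difference. It does not prevent the form and cut from being chosen after the pooled scores are seen.

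Fourth, the outcome is secondary, its main analysis is already continuous, and the plan commonly dichotomises its survey items. All true, and it limits the weight of the point. But those other splits are main analyses, and the score cuts quoted above are fixed.

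**Conclusion.** The fallback should be rewritten. Its trigger has no meaning in the stated model. If non-normality is meant, it is not reconciled with the transformation rule in both documents, and it leaves the cut-point open. A method that needs no cut-point is already among the plan's models.

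The size is conditional. With near-normal scores, an unchanged design effect and the printed 80% power at 0.25 SD, a split reduces power to about 61% (median) or 50% (20/80). For other shapes no single figure applies; the result turns on the cut. A reader might also infer that the fallback is likely to be used because such scales are often skewed. Nothing in the documents supports that, since they report only an SD for this scale. If the fallback is never triggered, the plan's power statement is unaffected.

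**What to change.** Replace the second sentence of the SAP entry with wording such as:

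> If residuals are clearly non-normal, decisional conflict will be analysed with the mixed-effects proportional-odds model (grouping sparse scores if needed), with the mean difference also reported; this replaces the general transformation rule for this outcome.

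Name the residual check, and make it on data pooled over arms. Any binary summary should be descriptive only, at a cut-point fixed before unblinding. The last clause of the wording is needed: deleting the dichotomisation sentence and simply keeping the mean difference would leave the general transformation rule pointing the other way, and the mean difference performs poorly under a floor spike (35–58% power in the cases tried, against 68–70% for the rank test).

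The cost is one sentence and no new method. When the fallback is used, the effect is an odds ratio rather than a difference in mean score, which is why the mean difference should be shown beside it. Some power is given up in one situation, a pure floor effect where the cut would have been at the floor (about 79% against 68–70%).
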